Potential participants for the pilot study will be identified through the Addiction Consult Service (ACS). [name] (co-I) will work with the research staff and clinical team to help identify patients for the PN to approach for screening. Research staff (patient navigator and research coordinator) will also review the Addiction Consult Service's patient list and information in the electronic health record (EHR) to perform "pre-screening" where potentially eligible participants are identified. Potentially eligible patients will be approached by the research coordinator. If the patient is eligible and agrees to participate in the study, then the research staff will obtain written informed consent, conduct the baseline assessment, and then randomize the patient using a REDCap randomization module. The study will aim to enroll 40 patients for the Aim 1 pilot RCT (20 randomized to each condition).

Pre-Screening Methods

Pre-screening Electronic Health Record Charts of Potential Participants:

Potential participants for the pilot study will be identified through the Addiction Consult Service. [name] (co-I) will work with the research staff and clinical team to help identify patients for the PN to approach for screening. Research staff (patient navigator and research coordinator) will also review the Addiction Consult Service's patient list and information in the electronic health record (EHR) to perform "pre-screening" where potentially eligible participants are identified.

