| Post-discharge EMR review form | | X | |
| Video submission review form | | X | X |
| 30-days post-discharge assessment | | | X |

After the assessment and randomization, the research staff member should review and check off the items in the Research Checklist that is provided at the end of the study assessment in REDCap and on paper, and once back in the Pat Steel Building office should file all paper forms in their appropriate locations:

- Disbursed reloadable credit card to participant
- Incentive receipt form signed by participant, physical copy with research staff
- Entered data into REDCap
- Consent signed by participant, (one copy given to participant, one copy filed, signature and date checked prior)
- HIPAA Authorization form signed by participant, in hand
- Contact form and ROI completed, in hand
- Phone agreement contract signed by participant (for those randomized to PN+mHealth), in hand

Randomization

Once a participant has signed the informed consent form, HIPAA Authorization form, provided contact information for the participant locator form, and completed the baseline assessment, the research study member who consented the participant can move forward with randomizing the participant to either the treatment as usual (TAU) or MIAPP study conditions. When explaining randomization, the research staff informs the participant that the decision of which condition they are assigned to is random – like the flip of a coin – and that the research team does not control who is in which condition. Participants

should only be randomized if they are able to complete the entire baseline assessment. Research staff will notify the participant of condition assignment immediately after the randomization is completed. Details about completing the randomization process through REDCap can be found in the MIAPP REDCap Manual of Procedures.

Treatment as Usual

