Participants randomized to the MIAPP intervention will utilize their personal smartphones or tablets, or be provided with a smartphone for use during the study period if they do not have access to a personal device or choose not to use their personal device. The patient navigator or other research staff will help patients obtain a study phone when needed. Phones will be returned at the end of the study period. Participants needing a study phone will sign two copies of a [Phone Agreement Contract](#). If the study phone is lost, damaged, or stolen, there is no penalty to the participant; the study phone will be replaced up to one time. If the second phone is lost, damaged, or stolen, participants can continue to upload videos using a personal device if able and willing. Alternatively, they can continue participating in all remaining study procedures without uploading videos – i.e., they can receive a financial reward for linking to an outpatient buprenorphine provider, and they can complete the 30-day follow-up assessment. Participants who choose to utilize their own device will not be reimbursed for data plan costs and will utilize their device's memory.

Protection of Human Subjects

Involvement of Human Subjects

This study will conduct a randomized controlled trial of 40 participants with opioid and methamphetamine use at Harborview Medical Center (HMC) who are initiated on buprenorphine while in the hospital to determine effects of the intervention on post-discharge outcomes of linkage to outpatient treatment, retention on medication, use of opioids or methamphetamine, and hospital

readmissions and ED visits. Patients will be assigned to one of two arms (20 per arm) using a stratified randomization procedure.

Research Material Obtained from Participants

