Descriptive statistics will be calculated for all baseline variables; variables will be assessed for any differences between the two randomized arms using chi-square tests, t-tests, or the Mann-Whitney U test depending on the distributions. Baseline variables that differ between the two arms and potentially confound tests of intervention effects will be included in analyses as covariates. This study will use an intent-to-treat analysis including all subjects according to their randomized assignment, regardless of their follow-up status and their level of compliance with intervention components. The investigators will provide regular written reports to the Data Safety Monitoring Board including outcome data by the unblinded treatment group.

Primary Outcome Analyses

We hypothesize that participants randomized to MIAPP + treatment as usual compared to treatment as usual alone will be more likely to link to outpatient treatment with medications for OUD within the 30 days of hospital discharge. To evaluate the primary hypothesis, we will use modified Poisson regression analysis (53) with robust standard errors to compare intervention arms on the proportion of participants who link to outpatient treatment with medications for OUD within 30 days of hospital discharge, while potentially controlling for any baseline variables that differ between the two groups as described above if they could confound the hypothesis test. The results of this analysis will be presented as the proportion of patients in each group who link to outpatient treatment and the (adjusted) risk ratio (RR, i.e., ratio of the two proportions) with a 95% confidence interval computed by exponentially transforming the coefficient of the treatment effect in the modified Poisson regression model. We will also report the difference between proportions with a 95% confidence interval, as recommended by CONSORT guidelines (54). The RR and difference are two different ways of quantifying the intervention effect that have meaningful clinical interpretations. Results from the Poisson regression will be used for primary interpretation and conclusions.

Secondary Outcome Analyses

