We hypothesize that participants randomized to MIAPP + treatment as usual compared to treatment as usual alone will a) have more days of medications for OUD treatment within the 90 days post-discharge (secondary), b) have lower rates of readmissions to the hospital and emergency department visits within 90 days (exploratory), and c) have fewer days using opioids or methamphetamine 30 days post-hospital discharge (exploratory). Analyses of secondary outcomes will use modified Poisson regression similar to those described above for binary outcomes (readmissions to hospital and emergency department) and linear regression for continuous outcomes (e.g., days of medications for OUD treatment; days of opioid or methamphetamine use).

Sample Size and Power

The primary goal of this pilot trial is to develop and pilot test the MIAPP intervention. This pilot work will provide evidence of the feasibility/acceptability of the MIAPP intervention and research procedures that will be used to inform a future, larger study, as assessed by our ability to fully recruit the planned sample and deliver the intervention to the majority of those randomized to the intervention arm. The sample size of 40 for the pilot randomized controlled trial was chosen as we projected we could enroll and complete the study procedures and analyses within the available funding period. Although the sample size was not selected for the purpose of providing a fully-powered study, with our sample size of 40 we are nonetheless powered at 80% to detect some effects if they are large in size. For binary outcomes, power depends on the base rate of the outcome measured, and based on prior studies (38, 55), we anticipate that anywhere from 20% to 50% of participants in treatment as usual successfully linking to outpatient medications for OUD services post-discharge. For binary outcomes, including the primary outcome measure, our pilot study will be powered to detect intervention effect sizes of $RR \geq 1.89, 2.05, 2.40, \text{ or } 3.10$, if linkage rates for treatment as usual are 50%, 40%, 30%, or 20%, respectively.

For continuous outcomes (days of buprenorphine coverage, days of opioid or methamphetamine use), we will be powered to detect standardized effect sizes of Cohen's $d \geq 0.91$ with 40 participants.

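### Randomization is called stratified, but the factors are not named and the covariate rule tends to leave them out of the models; if they are prognostic, the analysis is conservative

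*Combined protocol and SAP*

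**What the plan says.** Stratification is mentioned once, under Protection of Human Subjects, Involvement of Human Subjects: "Patients will be assigned to one of two arms (20 per arm) using a stratified randomization procedure". The Overview of Screening and Recruitment says only that staff will consent and assess the patient and "then randomize the patient using a REDCap randomization module". The Randomization section adds: "Details about completing the randomization process through REDCap can be found in the MIAPP REDCap Manual of Procedures". That manual is not part of the document. The factors, the number of strata and the block size appear nowhere.

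The opening paragraph of the Statistical Analysis Plan compares the arms on baseline variables by significance tests and then states: "Baseline variables that differ between the two arms and potentially confound tests of intervention effects will be included in analyses as covariates". For linkage within 30 days, Primary Outcome Analyses says "we will use modified Poisson regression analysis (53) with robust standard errors to compare intervention arms", "while potentially controlling for any baseline variables that differ between the two groups as described above if they could confound the hypothesis test". Secondary Outcome Analyses says: "Analyses of secondary outcomes will use modified Poisson regression similar to those described above for binary outcomes". It assigns linear regression to the continuous outcomes. No model is specified to contain a stratification factor.

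**The concern.** The design and the covariate rule pull against each other. A variable enters a model only if it differs between arms and could confound. A stratification factor is balanced by construction, so it tends to fail the first condition, and the better the stratification works, the more surely the factor is left out.

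When a factor predicts outcome and allocation is balanced within its levels, the treatment estimate varies less from trial to trial than under simple randomization. A model without the factor does not credit that gain in its standard error. The interval is then wider than needed and the test rejects less often than it could. Primary Outcome Analyses bases the main conclusions on the Poisson result, so the width of that interval matters even in a pilot.

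**Working it through.** **Inputs from the documents.** 20 per arm; modified Poisson with robust standard errors for binary outcomes; linear regression for continuous outcomes; treatment-as-usual linkage between 20% and 50%; a detectable Cohen's d of 0.91 (Sample Size and Power).

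**Assumptions.** Two-sided 5% level (consistent with the planned 95% interval); one binary factor with 20 patients in each stratum; exactly 10 + 10 allocated within each stratum; the stratum linkage rates below. The documents give no value for prognostic strength, so a range is shown.

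**1. The plan's own figure.** A two-sample t-test with 20 per arm has 80% power at d = 0.909, and d = 0.91 gives 80.1%. The stated 0.91 reproduces. It uses no stratum.

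**2. Linear regression.** Let R² be the share of within-arm variance explained by the strata. In units of the within-arm SD, the unadjusted model reports a standard error of about √(1/20 + 1/20) = 0.316. The adjusted one is about 0.316 × √(1 − R²). At R² = 0.20 this is 0.316 × 0.894 = 0.283. Simulated at d = 0.91 (8,000 trials):

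| R² | Power, unadjusted | Power, adjusted | Null rejection, unadjusted | Null rejection, adjusted |
|---|---|---|---|---|
| 0 | 79.7% | 79.8% | 5.1% | 5.2% |
| 0.05 | 80.4% | 81.8% | 4.2% | 4.8% |
| 0.10 | 81.4% | 84.1% | 4.4% | 5.6% |
| 0.20 | 83.2% | 88.2% | 3.0% | 5.4% |
| 0.30 | 83.6% | 91.8% | 2.0% | 5.1% |

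The adjusted null rates scatter around 5% within simulation error.

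**3. Primary model, risk ratio 1.6.** Treatment-as-usual linkage averages 40% in every row, inside the plan's range (4,000 trials; simulation error of one power figure about √(0.28 × 0.72 / 4000) = 0.7 points):

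| Linkage by stratum | Unadjusted | Adjusted | Difference (points) |
|---|---|---|---|
| 40% / 40% | 29.2% | 29.7% | 0.5 |
| 35% / 45% | 28.3% | 29.0% | 0.7 |
| 30% / 50% | 28.4% | 31.1% | 2.7 |
| 25% / 55% | 27.3% | 33.4% | 6.1 |
| 20% / 60% | 26.5% | 40.4% | 13.9 |

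Separate runs of 5,000 and 8,000 trials agree: 30% and 30% at 40%/40%; 30% and 32% at 30%/50%; 28% and 34–35% at 25%/55%; 25–26% and 39% at 20%/60%. Taken together the loss is about 0, 3, 6 and 13 points at 40%/40%, 30%/50%, 25%/55% and 20%/60%.

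**4. Near the plan's 30% scenario.** With stratum rates of 20%/40% and the plan's risk ratio of 2.40, power is 76.8% unadjusted and 81.2% adjusted, a difference of 4.4 points. With 30%/30% it is 74.4% and 74.7%.

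**5. What changes is the reported standard error.** With exact balance the log risk ratio has the same empirical SD with and without the factor. At 20%/60% and risk ratio 1.6 that SD is 0.299; the median reported standard error is 0.329 unadjusted and 0.274 adjusted. For an estimate of 1.6:
- unadjusted: exp(1.96 × 0.329) = 1.91, interval 1.6/1.91 to 1.6 × 1.91, or 0.84 to 3.06;
- adjusted: exp(1.96 × 0.274) = 1.71, interval 0.94 to 2.74.

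At 20%/40% and risk ratio 2.4 the figures are 0.372 unadjusted, 0.352 adjusted and an SD of 0.401.

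**6. Null rejection, modified Poisson.** At 20%/60%: 2.1% unadjusted, 3.6% adjusted. A non-prognostic factor gave 2.7% to 3.8% in different runs. Adjusted rates were 2.4% to 3.8% over all scenarios, never above 5%.

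**7. Cost of too many strata.** With four strata of 10, each with its own indicator, the chance that at least one stratum has no events under the null is 1 − (1 − 0.7¹⁰)⁴ = 11% at 30% linkage and 1 − (1 − 0.8¹⁰)⁴ = 37% at 20%. These match the convergence failures seen in simulation. With two binary factors entered as main effects, a whole level of 20 patients must be event-free, which has probability at most 4 × 0.7²⁰ = 0.3% and 4 × 0.8²⁰ = 4.6%.

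**The case against.** The factors are unnamed, so nothing shows that they predict outcome; if they do not, nothing is lost. That stands, and it is why the size is given as a range starting at zero. A reader might infer that the planned standard errors are too large and power is certainly lost, or that the factors must be prognostic because they were chosen for stratification. The documents support neither: they do not say what the factors are or why they were chosen.

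For the primary model, too large also needs care. The unadjusted robust standard error clearly exceeds the true SD only for a strong factor (0.329 against 0.299). At 20%/40% it lies below it (0.372 against 0.401), though still above the adjusted value.

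Nor should the 2.1% null rejection be put down wholly to omitted strata. Of the gap of 5 − 2.1 = 2.9 points, adjustment removes 3.6 − 2.1 = 1.5, about half. The rest is small-sample behaviour, present even with a non-prognostic factor.

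Finally, this is a pilot with a feasibility goal and was not sized for full power, and the error is on the safe side. That limits the consequence. It does not remove the conflict between a stratified design and a rule that screens out the strata.

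**Conclusion.** The point holds in conditional form. Allocation is described as stratified, the factors are not named, and the only covariate rule tends to exclude them. If they are prognostic, the primary analysis is conservative. Under the assumptions above (one binary factor, exact balance, risk ratio 1.6) the loss is about 0 points of power for a non-prognostic factor, 3 at 30%/50%, 6 at 25%/55% and 13 at 20%/60%. For continuous outcomes at d = 0.91 it is about 5 points at R² = 0.20 and 8 at R² = 0.30. Type I error is not inflated, so the plan is not invalid. The change is worth making because it is cheap, costs almost nothing if the factors turn out not to matter, and removes a discretionary choice from the primary model.

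**What to change.** In the Statistical Analysis Plan, name the stratification factor(s) and levels used in the REDCap module. State that they enter the primary, secondary and exploratory models as prespecified covariates regardless of observed balance, so that the rule based on differences between arms no longer decides their inclusion.

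Add a fallback for the modified Poisson model when a stratum has no events: for example, main-effects terms in place of one indicator per stratum, collapsed strata, or a Mantel-Haenszel risk ratio. Fix the order of these in advance. With 40 patients, few strata are preferable.

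The cost is two or three sentences. No new data are needed, since a factor used to allocate must already be recorded. The small downside is the convergence risk in step 7, which the fallback covers.

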Loss of confidentiality is very unlikely given the structures that will be put in place to avoid inadvertent disclosure. These structures to assure confidentiality include the following: each subject will receive a unique identification number, and research data collection and data entry forms will be electronic and identified only with this number. Only the master enrollment list, written informed consent forms, and participant locator information will have identifying information on them. These documents will be kept in a secure computer hard drive or in a locked file cabinet, accessible only to the Principal Investigator ([name]) and the Research Coordinator. Tracking information will be kept similarly. Computer data will be password protected and accessible only to research staff needing the information for follow-up and monitoring purposes. Files stored on UW servers will be protected by electronic firewalls that restrict access to designated users.

Another possible threat to confidentiality could arise if a participant indicates an imminent danger to self or others or if a participant discloses abuse of vulnerable persons such as children, the elderly, or the disabled. Ethical and legal requirements may force us to disclose this type of information to relevant authorities. We will attempt to minimize this threat to confidentiality by clearly informing participants of the risks involved during the informed consent process.

Potential Benefits

There are no known health benefits to subjects from participation in the proposed study. All subjects may benefit from discussing their health with an assessor.

Importance of Knowledge to be Gained

The study will inform us about the ability of an intervention that combines Patient Navigation with an mHealth adherence tool with video-DOT and financial incentives to improve adherence and retention for patients with opioid and methamphetamine use who have initiated buprenorphine for treatment of opioid use disorder while hospitalized. If the study demonstrates a benefit of the intervention, then this would provide evidence of efficacy of a new adjunct for opioid and methamphetamine use disorder treatment that could improve patient outcomes. The risks to subjects are reasonable in relation to

anticipated benefits and in relation to the importance of the knowledge expected to result from the proposed study.

Scene Health

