This Adverse Event Form includes the date of the event, what occurred, actions taken by project staff, planned follow up (if any), the intervention condition/study arm of the affected participant, whether the event appears to be related to the intervention, the seriousness of the event, and whether participant will continue in the study (see appendix). All AEs experienced by the participant during the time frame specified in the protocol (e.g., from the time of enrollment through the end of the study intervention period) are to be reported.

Please note that the AE form contains a column to indicate whether the event is serious. Thus, SAEs are a subset of the reported AEs.

Serious Adverse Event Reporting

All SAEs, unless otherwise specified in the protocol and approved by the IRB or DSMB (as applicable), require expedited reporting by the Principal Investigator to the study's safety monitoring bodies. Serious adverse events will be reported to the site PI within 24 hours of research staff becoming aware of the event. SAEs that are unanticipated problems will be reported to the NIDA PO and DSMB Chair within 24 business hours of becoming aware by email and a written follow up will be submitted within 2 days of awareness of the event; reporting/submitting supplemental forms to UW should be according to most current requirement, currently within 10 business days (within 24 hours if there was a breach of confidentiality).

Any IRB action response will be reported to NIDA PO within 3 days of the receipt of notice of the action.

Suicidality

It is possible that participants may disclose suicidal ideations (SI) with research staff when conducting study activities. Any participant who voices current suicidality or is experiencing a psychiatric emergency

at study visit will be reported to the site PI, or another doctor on-site, immediately. That physician will determine the appropriate course of action, which will depend on the clinical situation.

Patient Health Questionnaire-9 (PHQ-9)

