The PHQ-9 is administered at the study baseline visit and the 30-day post discharge follow-up visit. Question number 9 of the PHQ-9 asks the participant: *“Over the past 2 weeks, how often have you been bothered by any of the following problems? Thoughts that you would be better off dead, or thoughts of hurting yourself in some way?”* If a participant answers the question with an answer of “several days,” “more than half the days,” or “nearly every day” research staff then ask the participant the below follow-up questions:

1. "Which of the two statements, ‘better off dead’ or ‘thoughts of hurting yourself’ were you endorsing?”
2. If yes to “thoughts of hurting yourself,” ask follow-up question “are you currently (i.e. right now) having those thoughts?”
3. If answer to question #2 is “no,” respond by saying “I’m glad to hear that” and research staff will provide information for the 988 Suicide and Crisis Hotline and emphasize that the participant can go to the Emergency Department or inform their current medical providers for help.
4. If answer to question #2 is “yes,” the PI and one of the study medical providers will be notified immediately for assessment.

If a participant indicates current SI to research staff during a remote interaction, such as a phone call or video chat session, the research staff will remain on the phone with the participant to: (1) provide encouragement to utilize the 988 Suicide and Crisis Hotline, (2) encourage the participant to visit the Emergency Department if they believe they may act on suicidal or self-harm thoughts, and (3) notify the study PI or a medical provider on site, who will determine the course of action.

Data Safety and Monitoring Plan

The Principal Investigator (PI) will be responsible for ensuring participants’ safety on a daily basis. The PI [name] and a Data Safety Monitoring Board (DSMB) will oversee the safety of the participants and the validity and integrity of the data. The DSMB will be led by an individual who is selected at the discretion of the funding agency and [name]. Individual members of the DSMB will be named at the time of award.

Responsibilities of the DSMB

Responsibilities will include:

- Evaluating the research protocols and plans for safety and data monitoring prior to start of participant enrollment

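### The PHQ-9 item 9 script stops after its first question for a participant who endorses only 'better off dead', without even the hotline information

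*Combined protocol and SAP*

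**What the plan says.** The section Patient Health Questionnaire-9 (PHQ-9) says the instrument is given at baseline and at the 30-day post-discharge visit. Item 9 combines two ideas, being better off dead and hurting oneself. Any answer from several days upward leads to four numbered steps:

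1. Staff ask which of the two ideas the participant had in mind.
2. The next question is conditional: "If yes to “thoughts of hurting yourself,” ask follow-up question “are you currently (i.e. right now) having those thoughts".
3. If the answer to step 2 is no, "research staff will provide information for the 988 Suicide and Crisis Hotline and emphasize that the participant can go to the Emergency Department"; telling one's own clinicians is offered as an alternative.
4. If the answer to step 2 is yes, "the PI and one of the study medical providers will be notified immediately for assessment".

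A separate paragraph covers remote contact and begins: "If a participant indicates current SI to research staff during a remote interaction". Staff then stay on the line, encourage use of 988 and the Emergency Department, and notify the PI or a provider.

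The Suicidality section just before it sets a general rule, whose scope is: "Any participant who voices current suicidality or is experiencing a psychiatric emergency". When this happens during a visit, staff must tell the PI or a physician who is present straight away.

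**The concern.** The trigger for the script is a positive answer to either half of item 9, but every step after step 1 is reserved for one half. The protocol treats a 'better off dead' answer as needing follow-up, asks one question about it, and then gives the interviewer no instruction.

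The resulting order is hard to justify. Someone who has had self-harm thoughts but denies them now is given the hotline, Emergency Department and provider information. Someone who has felt better off dead nearly every day for two weeks is given nothing by the script.

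Two features of the study add weight:

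- **Setting at follow-up.** At baseline the participant is an inpatient. By the second PHQ-9 the participant has left hospital. The visit may be by telephone (Research Reimbursements and Incentives) and may take place up to 90 days after discharge (Follow-up Research Appointment).
- **No routine sharing with clinicians.** Under Data Collection Overview, study data do not go to clinicians outside the study team unless there are imminent safety concerns. The step 3 prompt to tell one's own providers is therefore the scripted way in which clinicians might learn of a non-imminent answer, and this participant does not receive it.

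**Working it through.** The plan gives no figure to reproduce. The check is a trace of each possible answer through the script, followed by a search for any other rule that would catch the missing case.

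**Inputs (PHQ-9 section).** Three actions can follow step 1: the question about current thoughts (step 2), the 988/Emergency Department/provider information (step 3), and notification (step 4). Step 2 requires endorsement of self-harm thoughts. Step 3 requires a no to step 2, and step 4 requires a yes.

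**Trace.**

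| Answer to step 1 | Answer to step 2 | Question | Information | Notification | Actions received |
|---|---|---|---|---|---|
| Self-harm thoughts, alone or with 'better off dead' | No | yes | yes | no | 2 of 3 |
| Self-harm thoughts, alone or with 'better off dead' | Yes | yes | no | yes | 2 of 3 |
| 'Better off dead' only | Not asked | no | no | no | 0 of 3 |

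Steps 3 and 4 exclude each other, so two is the most that any branch can reach at present. The count describes the script and is not a measure of risk. A participant who endorses both statements does reach step 2, so the gap is confined to the last row.

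**Other rules that might supply the step.**

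- *Suicidality section.* It requires suicidality voiced as current, or a psychiatric emergency, at a study visit. The script never asks this participant about current thoughts, so the rule depends on the participant volunteering it or on staff recognising it.
- *Remote paragraph of the PHQ-9 section.* It requires current ideation to be indicated, so the same limit applies.
- *Adequacy of Protection Against Risks, on confidentiality.* It addresses disclosure to authorities "if a participant indicates an imminent danger to self or others". It gives the participant no information.
- *Adequacy of Protection Against Risks, on distress.* Physician investigators are available if research procedures lead to consequences such as suicidal thoughts. Thoughts from the past two weeks reported on a questionnaire are not clearly such a consequence, and the clause gives the interviewer no step.

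None of these provides the 988, Emergency Department or provider information after an endorsement that is not voiced as current.

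**The case against.** The strongest reply is that the split is deliberate triage. Step 1 exists only to separate the two statements, which makes sense only if they are to be handled differently. This could explain not calling the PI. It does not readily explain leaving out a hotline number, the least burdensome action in the script, when someone who denies current self-harm thoughts is given it. Nothing in the documents requires that information after every positive answer, so this part is a judgement about good practice.

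The second reply is that the backstops are stronger than the trace suggests. The Suicidality section does not define current suicidality, and a trained interviewer could reasonably apply it to someone reporting such thoughts nearly every day. Step 1 also gives the participant an opening to say more. Staff are trained and supervised, and the remote paragraph covers telephone visits once current ideation is indicated. All of this stands and narrows the gap to 'better off dead' thoughts that are neither voiced nor recognised as current. It does not close it.

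Third, interviews are run from REDCap, and the follow-up section shows that procedural instructions are placed inside the REDCap assessment for at least one other measure. The PHQ-9 form may already prompt for this answer. That also stands: the finding is about the protocol text, and what happens in practice is unknown.

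Finally, the action count gives a handout and an immediate physician assessment equal weight. It should not be used to argue severity, and is not used that way here.

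**Conclusion.** The concern holds. As the protocol is written, a participant who endorses only 'better off dead' triggers the item 9 script and receives none of its three later actions, against two for a participant who endorses self-harm thoughts. The general rules mitigate this only when suicidality is voiced or recognised as current.

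Confidence in the reading of the text is high. It assumes that the numbered steps are the whole script; the REDCap forms and manual were not available. The documents do not say how often this answer is expected, so no number of the 40 planned participants is estimated.

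This is a participant-safety omission that should be corrected. It has no bearing on the primary outcome, the sample size, the analysis or the trial's conclusions.

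**What to change.** Amend the numbered steps as follows:

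- Give the 988, Emergency Department and current-provider information after any positive item 9 answer.
- Ask the question about current thoughts after endorsement of either statement.
- Retain step 4 notification for current self-harm thoughts.
- Have the study physicians and IRB set the escalation threshold for current 'better off dead' thoughts. A reasonable default is the same step 4 notification.

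A participant endorsing only 'better off dead' would then receive the question and the information (2 of 3 actions), plus notification if the thoughts are current and the default is adopted (3 of 3). Participants with current self-harm thoughts would also receive the information in addition to notification. If only a minimal change is wanted, a single line giving the step 3 information to 'better off dead' only participants closes the part of the gap that triage does not explain.

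The cost is a short text edit, a matching edit to the assessment form if it has the same branching, notice to the IRB, and possibly a few more notifications depending on the threshold. If REDCap already handles this answer, the protocol text need only be aligned with it.
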